### *Appendix 1d*

### *Schedule of Assessments: 12-week Safety Follow-Up After Completion or Early Termination of Open-Label Extension Phase*

Assessments	Week ( $\pm 3$ days)			Unscheduled Visit c
	Week 4 a	Week 8 a	Week 12 or Early Withdrawal Visit b	
Concomitant medications	x	x	x	x
Adverse events	x	x	x	x
Urine pregnancy test d			x	
Physical examination			x	
Anti-drug antibody sample (serum) e			x	
PML neurologic examination f			x	

ADA =anti-drug antibody; PD =pharmacodynamic; PK =pharmacokinetic; PML =progressive multifocal leukoencephalopathy.

a Week 4 and Week 8 study assessments are to be made by telephone call and not by clinic visit.

b All assessments indicated for the Early Withdrawal Visit should be performed if the patient discontinues prior to completion of the 12-week safety follow-up period.

c Unscheduled visit for safety monitoring.

d A urine test may be performed; however, if urine test result is positive, a confirmatory serum test must be performed. A urine pregnancy test is only required in female patients at Tanner Stage 2 or greater, or after onset of menarche. The test must be performed on a fresh voided sample.

e If serum sickness or a clinically significant allergic drug reaction is suspected, the Sponsor should be notified, and serum for the analysis of study drug level and ADA should be drawn. If etrolizumab concentrations or PD assessments are needed then ADA sample can be used.

f PML neurologic examination consists of the PML Subjective Checklist. Administer before other assessments as per [Appendix 7](#).

**Appendix 1e**  
**Schedule of Assessments: Progressive Multifocal  
Leukoencephalopathy Monitoring Phase**

	Extended PML Monitoring Phase a	
Assessments	24, 48, 68, and 92 b Weeks after Discontinuation from Study Treatment c OR Symptom-Driven Unscheduled Telephone Call d OR Early Termination e, f OR After Completion of OLE g	Unscheduled Visit h
PML Subjective Checklist i	x	x
Adverse event reporting to the Sponsor j	x	x

OLE=open-label extension; PML=progressive multifocal leukoencephalopathy.

Note: The extended PML monitoring period is to be conducted for patients completing or discontinuing from the randomized treatment phase after completion of the safety follow-up AND for patients entering *or discontinuing* from the open-label extension phase.

- a The total length of the PML monitoring period is 104 weeks. The extended PML monitoring period telephone calls will occur at the indicated timepoints for the extended PML monitoring period. The extended PML monitoring will be conducted using a PML Subjective Checklist over the telephone. PML monitoring should occur within 7 days of the specified day.
- b Patients that complete the 24-week treatment phase but do not enter the OLE phase. The last PML monitoring call will be 92 weeks after completion of the randomized treatment phase. For patients that discontinue early from the treatment phase, the last PML monitoring call will be 96 weeks after discontinuation. For the patients that complete OLE, the last PML monitoring call will be 104 weeks after OLE completion.
- c For patients that complete the treatment phase, the PML monitoring phase includes Week 12 to Week 16 of the treatment phase plus the 8-week safety follow-up and the 92-week PML safety monitoring phase.
- d Unscheduled telephone call represents a call that is not as per Schedule of Assessments and it is symptom driven.
- e For patients that discontinue early from the 24-week randomized treatment phase, the PML monitoring phase includes 8-week safety follow up and 96 weeks of PML safety monitoring.
- f For patients that discontinue after the 24-week randomized treatment phase but prior to study completion (end of extended PML monitoring period), the early termination visit from the extended PML monitoring period should be performed (a subjective checklist by telephone).
- g For patients that complete the OLE *treatment*, the PML monitoring phase includes 104 weeks of PML safety monitoring.
- h Unscheduled visit represents a visit that is not as per Schedule of Assessments and it is symptom driven.
- i If there are any signs or symptoms suggestive of PML identified on the subjective checklist during the telephone call, the patient will be asked to come into the clinic for further evaluation and if indicated referral to a neurologist. .
- j Investigators are not required to actively monitor patients for adverse events; however, if he or she becomes aware of any other serious adverse events that are believed to be related to prior study drug treatment, these should be reported directly to Roche or its designee either by faxing or by scanning and e-mailing the Serious Adverse Event/Adverse Event of Special Interest Reporting Form with use of the fax number or e-mail address provided to the investigators. The investigator may become aware of such events at these timepoints or via other means, but the data are not to be collected routinely.

**Appendix 2**  
**Pediatric Ulcerative Colitis Activity Index (PUCAI)**

ITEM	POINTS
1. Abdominal pain:	
No pain	0
Pain can be ignored	5
Pain cannot be ignored	10
2. Rectal bleeding	
None	0
Small amount only, in less than 50% of stools	10
Large amount (>50% of the stool content)	20
Small amount with most stools	30
3. Stool consistency of most stools	
Formed	0
Partially formed	5
Completely unformed	10
4. Number of stools per 24 hours	
0-2	0
3-5	5
6-8	10
>8	15
5. Nocturnal bowel movement (any diarrhea episode causing wakening)	
No	0
Yes	10
6. Activity level	
No limitation of activity	0
Occasional limitation of activity	5
Severe restricted activity	10
SUM OF PUCAI (0-85)	

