**Table 1 Objectives and Corresponding Endpoints for the Randomized Treatment Phase**

Primary Objective	Corresponding Endpoints

 
To evaluate the pharmacokinetics and pharmacodynamics of etrolizumab in a pediatric IBD patient population
 
	
 
PK parameters: <math>C_{max}</math>, <math>AUC_{tau}</math>, <math>t_{1/2}</math>, <math>C_{trough}</math>
 
PD parameters: <math>\beta 7</math> receptor occupancy by flow cytometry on peripheral blood lymphocytes
 

Safety Objective	Corresponding Endpoints

 
To evaluate the overall safety and tolerability of etrolizumab in pediatric population
 
	
 
Incidence and severity of infection-related adverse events
 
Incidence of immunogenic responses (ADAs)
 
Incidence and severity of hypersensitivity reaction events
 

Exploratory Objectives	Corresponding Endpoints

 
To evaluate additional pharmacodynamic biomarkers of etrolizumab
 
To evaluate clinical disease biomarkers with etrolizumab treatment
 
To evaluate the clinical efficacy of etrolizumab
 
	
 
Changes in serum MAdCAM-1
 
Changes in serum CRP and fecal calprotectin
 
Clinical response at Week 16, as assessed by the PUCAI (UC) and PCDAI (CD)
 

ADA=anti-drug antibody;  $AUC_{tau}$ =area under the concentration–time curve within a dosing interval; CD=Crohn's disease;  $C_{max}$ =maximum concentration observed; CRP=C-reactive protein;  $C_{trough}$ =steady-state concentration at the end of a dosing interval; MAdCAM-1=mucosal vascular addressin cell adhesion molecule-1; PD=pharmacodynamic; PK=pharmacokinetic; PCDAI=Pediatric Crohn's Disease Activity Index; PUCAI=Pediatric Ulcerative Colitis Activity Index;  $t_{1/2}$ =elimination half-life.

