**Table 2 Objectives and Corresponding Endpoints for the Open-label Extension Phase**

Safety Objective	Corresponding Endpoints

 
To evaluate long-term safety of etrolizumab in pediatric population
 
	
 
Incidence and severity of infection-related adverse events
 
Incidence and severity of malignancies
 
Incidence of ADAs to etrolizumab
 
Incidence and severity of hypersensitivity reactions
 

Efficacy Objective	Corresponding Endpoint

 
To evaluate long term efficacy of etrolizumab in pediatric population
 
	
 
Clinical response at Week 132, as assessed by the PUCAI (UC) and PCDAI (CD)
 

ADA=anti-drug antibody; CD=Crohn's disease; OLE=open-label extension; PCDAI=Pediatric Crohn's Disease Activity Index; PUCAI=Pediatric Ulcerative Colitis Activity Index; UC=ulcerative colitis.

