#### **Pediatric Ulcerative Colitis Activity Index (PUCAI)**

The PUCAI quantifies the signs and symptoms of patients with UC (see [Appendix 2](#)). The components of the PUCAI include patient- or caregiver-reported abdominal pain, rectal bleeding, stool consistency, number of stools, nocturnal stools, and activity level on average over the past two days (Turner et al. 2007). These signs and symptoms are reported by patients (age  $\geq 7$  years), or caregivers of patients  $< 7$  years of age, via worksheets or an interview with the clinician, and the remaining components are completed by the physician. A numerical value is assigned to each response; responses are summed to a total score of 0-85, with a higher score indicating more severe disease. Please refer to [Appendix 2](#) for details.

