## **6.9 EXPLORATORY ANALYSES**

PUCAI/PCDAI response or remission rates will be summarized descriptively over time within each treatment group. Disease activity scores and subscores, fecal calprotectin levels and serum CRP levels and their change from baseline will also be summarized descriptively over time to assess the efficacy of etrolizumab in reducing signs and symptoms of disease and levels of inflammatory biomarkers.

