## **7. DATA COLLECTION AND MANAGEMENT**

### **7.1 DATA QUALITY ASSURANCE**

The Sponsor will be responsible for data management of this study, including quality checking of the data. Data entered manually will be collected via EDC through use of eCRFs. Sites will be responsible for data entry into the EDC system. In the event of discrepant data, the Sponsor will request data clarification from the sites, which the sites will resolve electronically in the EDC system.

The Sponsor will produce an EDC Study Specification document that describes the quality checking to be performed on the data. Central laboratory data will be sent directly to the Sponsor, using the Sponsor's standard procedures to handle and process the electronic transfer of these data.

eCRFs and correction documentation will be maintained in the EDC system's audit trail. System backups for data stored by the Sponsor and records retention for the study data will be consistent with the Sponsor's standard procedures.

COA data will be collected on paper questionnaires that may be administered via interview with the clinician. The data from the questionnaires will be entered into the EDC system by site staff.

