#### **PUCAI definitions of disease activity, remission, and response to therapy** (all are based on analysis of data generated during development process during 2006)

- **Remission:** total score less than 10 points
- **Mild disease activity:** total score between 10 and 30 points inclusive
- **Moderate disease activity:** total score between 35 and 60 points inclusive
- **Severe disease activity:** total score of 65 points or greater
- **Response** (minimal clinically significant change in score over time): a change in score of at least 20 points.

## Appendix 3

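### The Appendix 2 PUCAI form appears to exchange the points of its two heaviest rectal-bleeding categories, so some UC responses would be misclassified

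*Combined protocol and SAP*

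**What the plan says.** Appendix 2 prints four categories for item 2, rectal bleeding. No bleeding scores 0, and a small amount in under half of stools scores 10. "Large amount (>50% of the stool content" scores 20 and "Small amount with most stools" scores 30. The items sum to a total of 0 to 85, which Section 4.5.9 describes as a score "with a higher score indicating more severe disease".

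The response definition at the end of Appendix 2 is "a change in score of at least 20 points". Remission is a total below 10.

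The score feeds two named endpoints:
- Table 1, exploratory: "Clinical response at Week 16, as assessed by the PUCAI (UC) and PCDAI (CD"
- Table 2, efficacy in the open-label extension: "Clinical response at Week 132, as assessed by the PUCAI (UC) and PCDAI (CD"

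Section 6.9 states that "PUCAI/PCDAI response or remission rates will be summarized descriptively over time within each treatment group", and it also summarizes scores and subscores over time. Section 7.1 says the instruments are completed on paper and that "The data from the questionnaires will be entered into the EDC system by site staff".

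**The concern.** As printed, a child passing a large amount of blood scores 10 points less than a child with a small amount in most stools. That runs against the stated direction of the scale. It is also the only such case on the form: in abdominal pain, stool consistency, stool number, nocturnal stools and activity level, every worse category carries more points. The Appendix 2 user guide clarifies the time window, the activity levels and the score definitions. It says nothing about bleeding, and for most items it refers the rater back to the instructions on the form.

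Rectal bleeding is the heaviest item, at 30 of 85 points, and an error of 10 or 20 points is half or all of the response threshold. A child who bled heavily at baseline and improved can be counted as a non-responder, and the reverse can also occur. The plan describes no step that would detect the inversion.

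**Working it through.** **Inputs.** Item points, the 20-point response rule and the remission cut-off come from Appendix 2. The direction of the scale comes from Section 4.5.9.

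Labels for the bleeding categories: N = none, S = small in under half of stools, M = small in most stools, L = large.

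| Category | Printed points | Points in severity order |
|---|---|---|
| N | 0 | 0 |
| S | 10 | 10 |
| M | 30 | 20 |
| L | 20 | 30 |

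**The plan's own total.** The item maxima sum to 10 + 30 + 10 + 15 + 10 + 10 = 85. This reproduces the stated range, and it is 85 under either assignment, so the total cannot reveal the exchange.

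**Error in the change score.** Change = follow-up minus baseline, and error = printed change minus ordered change.

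| Transition | Printed | Ordered | Error |
|---|---|---|---|
| N to M | +30 | +20 | +10 |
| N to L | +20 | +30 | −10 |
| S to M | +20 | +10 | +10 |
| S to L | +10 | +20 | −10 |
| M to N | −30 | −20 | −10 |
| M to S | −20 | −10 | −10 |
| L to N | −20 | −30 | +10 |
| L to S | −10 | −20 | +10 |
| L to M | +10 | −10 | +20 |
| M to L | −10 | +10 | −20 |

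The other six of the 16 transitions (four with no change of category, plus N to S and S to N) have no error. The absolute error is therefore 0 in 6, 10 in 8 and 20 in 2.

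**Effect on response.** Let d be the summed change in the other five items, with negative values meaning improvement. Response is taken as bleeding change + d ≤ −20. The main flips are:
- L to S, d = 0 or −5: false non-response. At d = 0, printed −10 against ordered −20.
- M to S, d = 0 or −5: false response. At d = 0, printed −20 against ordered −10.
- L to M, d = −10 to −25: false non-response. At d = −10, printed +10 − 10 = 0 against ordered −10 − 10 = −20.
- M to L, d = −10 to −25: false response. At d = −10, printed −10 − 10 = −20 against ordered +10 − 10 = 0.

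With the other items unchanged, only the first two flip. The two 20-point transitions need a gain of 10 to 25 points elsewhere. The remaining transitions with an error flip only when the other items worsen by 5 or 10 points (L to N, M to N) or improve by 30 to 45 points (N or S moving to M or L).

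**Effect on remission.** The other items have 3 × 3 × 4 × 2 × 3 = 216 combinations. With four bleeding categories that makes 216 × 4 = 864. Remission status changes in none of them, because M and L each score at least 20 under either assignment.

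**Effect of one misclassified child.** The documents do not give the UC/CD split. Assume 6 to 18 UC patients among about 24, split 1:1, so 3 to 9 per arm. One child is then 1/9 = 11% to 1/3 = 33% of an arm's UC patients.

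**The case against.** The strongest objection is that the text was machine-read from a PDF. The points run 0, 10, 20, 30, and only two adjacent labels look out of order, which is what a reading error would produce. That cannot be fully excluded, although the other rows and points on the form read cleanly. Inspecting the original page settles it.

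Second, the validated instrument is cited but not reproduced elsewhere, and the statement about direction in Section 4.5.9 describes the total, not each item. The item also mixes amount with frequency. This is a fair reason to keep the correction conditional. It does not explain why a large amount should score below a small one when the other five items rise throughout.

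Third, neither the worksheets nor the electronic scoring is in the documents, so nothing shows that collected data carry the error. Section 6.9 plans subscore summaries, which implies item-level data, and Section 7.5 requires paper outcome data to be retained. Any damage is probably recoverable.

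Fourth, the analyses concerned are descriptive, the Week 16 endpoint is exploratory, and no power calculation exists. That limits the stakes, but Week 132 response is the only efficacy endpoint listed for the extension.

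Finally, the 11 to 33 percentage points describe how small the arms are. They do not say how often the error occurs, and the 16 transitions are not equally likely. Both points stand: the figure is the leverage of one misclassified child and not a forecast.

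**Conclusion.** The concern holds. As printed, item 2 conflicts with the stated direction of the score and with the pattern of the rest of the form, and nothing in Appendix 2 resolves it. If the form is used as printed, UC change scores are wrong by 10 or 20 points in 10 of the 16 bleeding transitions. Response can then be misclassified in both directions at Week 16 and Week 132.

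Three assumptions carry this: the extracted text matches the original page, the intended points follow severity, and worksheets and scoring copy the form. The leverage figure also rests on the assumed UC split, and it applies to the randomized arms; all patients in the extension receive one regimen.

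The item should be fixed before PUCAI response is reported. Confidence is medium, because neither the original page nor the instrument could be inspected.

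**What to change.** 1. Check item 2 on the original page of Appendix 2 and against the validated instrument.
2. If the exchange is confirmed, correct the appendix so that a small amount in most stools scores 20 and a large amount scores 30.
3. Check the site worksheets, their translations and the scoring in the electronic data capture system for the same error.
4. Where they copied the form, re-derive totals from the item-level category answers before any PUCAI response, score or subscore is reported.
5. As a minor clarification, define response as a decrease from baseline of at least 20 points; the present wording gives no direction.

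The cost is an appendix correction, a document and database check and, if needed, a programmed re-score. No new data are needed where the category answers are kept on the paper questionnaires.

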## **Appendix 2** **Pediatric Ulcerative Colitis Activity Index (PUCAI) (cont.)**

### **PUCAI User Guide**

Most items contained in the PUCAI can be scored using the instructions provided within the instrument. The following issues require additional clarification.

#### **Time period for evaluation**

- Answers should reflect a daily average of the last two days.
- However, if clinical conditions are changing rapidly (e.g., during intense intravenous therapy), the previous 24 hours should be considered.
- For patients undergoing colonoscopy, answers should reflect the two days before bowel cleanout was started.

#### **Activity level**

- Occasional limitation of activity= could attend school or equivalent, but reduced activity (e.g., attends school but does not play at breaks).
- Severe restricted activity=could not attend school or equivalent activity.

#### **PUCAI definitions of disease activity, remission, and response to therapy** (all are based on analysis of data generated during development process during 2006)

- **Remission:** total score less than 10 points
- **Mild disease activity:** total score between 10 and 30 points inclusive
- **Moderate disease activity:** total score between 35 and 60 points inclusive
- **Severe disease activity:** total score of 65 points or greater
- **Response** (minimal clinically significant change in score over time): a change in score of at least 20 points.

## Appendix 3

### Pediatrics Crohn's Disease Activity Index (PCDAI)

ITEM	POINTS			
Abdominal pain				
None	0			
Mild (brief episodes, not interfering with activities)	5			
Moderate/severe (frequent or persistent, affecting with activities)	10			
Stools				
0-1 liquid stools, no blood	0			
2-5 liquid or up to 2 semi-formed with small blood	5			
Gross bleeding, >6 liquid stools or nocturnal diarrhoea	10			
Patient functioning, general well-being (Recall, 1 week)				
No limitation of activities, well	0			
Occasional difficulties in maintaining age appropriate activities, below par	5			
Frequent limitation of activities, very poor	10			
EXAMINATION				
Weight				
Weight gain or voluntary weight loss	0			
Involuntary weight loss 1-9%	5			
Weight loss >10%	10			
Height				
< 1 channel decrease (or height velocity > -SD)	0			
> 1<2 channel decrease (or height velocity < -1SD> -2SD)	5			
> 2 channel decrease (or height velocity < -2SD)	10			
Abdomen				
No tenderness, no mass	0			
Tenderness, or mass without tenderness	5			
Tenderness, involuntary guarding, definite mass	10			
Peri-rectal disease				
None, asymptomatic tags	0			
1-2 indolent fistula, scant drainage, tenderness of abscess	5			
Active fistula, drainage, tenderness or abscess	10			
Extra-intestinal manifestations				
Fever > 38.5 x 3 days in week, arthritis, uveitis, erythema nodosum, or pyoderma gangrenosum				
None	0			
One	5			
Two	10			
LABORATORY				
Hct (%)				
<10yrs	11-14 (male)	11-19 (female)	15-19 (male)	
> 33	> 35	> 34	> 37	0
28-33	30-34	29-33	32-36	2.5
< 28	< 30	< 29	< 32	5
ESR (mm/hr)				
< 20				0
20-50				2.5
> 50				5
Albumin (g/L)				
>35				0
31-34				5
<30				10

Disease activity

<10 – remission

10-27.5 – mild

30-37.5 – moderate

>40 – severe

TOTAL =

## **Appendix 4** **Anaphylaxis Precautions**

The following equipment is needed in the event of a suspected anaphylactic reaction during study drug administration:

- Monitoring devices: ECG monitor, blood pressure monitor, oxygen saturation monitor, and thermometer
- Oxygen
- Epinephrine for intravenous, intramuscular, and endotracheal administration in accordance with institutional guidelines
- Antihistamines
- Corticosteroids
- Intravenous infusion solutions, tubing, catheters, and tape

The following are the procedures to follow in the event of a suspected anaphylactic reaction during study drug administration:

- Stop the study drug infusion.
- Call for additional medical assistance.
- Maintain an adequate airway.
- Ensure that appropriate monitoring is in place, with continuous ECG and pulse oximetry monitoring, if possible.
- Administer antihistamines, epinephrine, or other medications as required by patient status and as directed by the physician in charge.
- Continue to observe the patient and document observations.
- Draw serum/plasma samples for immunogenicity testing.
- Ask patient to return for washout immunogenicity sample if appropriate.

## Appendix 5

### Tanner Stages

#### Sexual Maturity Stages in Boys and Girls

	Male Genitalia	Pubic Hair	Female Breasts
1	Preadolescent—testes, scrotum, and penis are childlike in size	Stage None; may be vellus hair, as over abdomen	Preadolescent—elevation of papilla only
2	Slight enlargement of scrotum with reddening of skin; little or no enlargement of penis	Sparse growth of long, slightly pigmented, downy hair, straight or slightly curled, primarily at base of penis or along labia	Breast bud stage; breast and papilla form a small mound; areolar diameter enlarges
3	Further enlargement of scrotum; penis enlarges, mainly in length	Hair considerably darker, coarser, and more curled; spreads sparsely over junction of pubes	Further enlargement of breast and areola with no separation of their contours
4	Further enlargement and darkening of scrotum; penis enlarges, especially in breadth; glans develops	Adult-type hair that does not extend onto thighs, covering a smaller area than in adult	Areola and papilla project to form a secondary mound above the contour of the breast; stage 4 development of the areolar mound does not occur in 10% of girls and is slight in 20%; when present, it may persist well into adulthood
5	Adult in size and shape	Adult in quantity and type with extension onto thighs but not up linea alba	Mature female; papilla projects and areola recesses to general contour of breast

Data from Tanner JM: Normal growth and techniques of growth assessment. Clin Endocrinol Metab 15:436, 1986.

In boys, if different scores are obtained for pubic hair and genitalia, the score for genitalia should be used.

In girls, if different scores are obtained for pubic hair and breast development, the score for breast development should be used.

